## 12.5 Study Site Selection and Pair Matching

We will use a parallel cluster randomized trial, in which random allocation to the experimental condition occurs at the site- (or cluster-) level rather than at the participant-level. Like other randomized designs, cluster randomized trials are methodologically rigorous and yield strong inferences about intervention effectiveness. Cluster randomized trials are well-suited to implementation research because participant-level randomization is often impractical with multi-faceted or structural interventions and is susceptible to contamination bias in this setting. The SSP vans currently serve 15 neighborhood sites across the city. We will select 12 of the sites to include in the cluster randomized trial. Several factors are relevant to site selection. We must consider proximity of the sites. If two sites are very close together, there may be contamination, where the intervention delivered at one of sites affects the proximal site as well. Where there is a high risk of overlap between two sites, we will exclude one of the sites or consider the two sites to be a single site in the trial.

Because the number of randomly allocated units in this cluster randomized trial is small, we anticipate using a matched-pair design. The idea is to identify pairs of sites that are similar to one another in important characteristics, with one site in each pair randomized to the intervention and the other site to usual care. To assess for good site pairings, we will review all available BCHD data about the different SSP sites – number of clients accessing services each week, client demographic characteristics, and HIV prevalence. Additionally, we will interview current SSP staff to capture qualitative aspects of the different sites. At the conclusion of this process we will identify 12 sites (6 pairs) for the trial. Of note, cohort recruitment at the sites will be staggered, whereby recruitment will begin at the first 2 pair (4 sites), then move to a second set of 2 pair, and finally to a third set of 2-pair.

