## 12.7 Analysis Plan

### 12.7.1 *Analysis plan for primary and secondary endpoints*

We will estimate the impact of the ICV on the composite primary outcome which incorporates the following: HIV prevention, testing, and treatment; HCV prevention, testing, and treatment; substance use and treatment; overdose; and healthcare utilization (see Appendix). We will also estimate the impact of the ICV on the separate measures that make up the composite outcome, including the HIV care cascade, the PrEP continuum, MAT engagement, and linkage to HCV treatment. The outcomes will be continuous (composite primary outcome), ordinal (HIV care cascade, PrEP continuum, HCV linkage), and dichotomous (MAT), and the analytic samples will vary depending on

the outcome. For all outcomes, the data will have the same structure, with time ( $t$ ) nested within participants ( $i$ ) nested within SSP sites ( $j$ ). The three-level structure of the data will induce correlations in the outcomes within sites and within participants, and this will be addressed by using random intercepts for site and random intercepts for participants. Fixed effects will include covariates for calendar time (a linear, quadratic, spline terms, or indicators as indicated by exploratory data analysis), indicator for 6-month follow-up assessment, a time-varying indicator for ICV exposure status, and follow-up-by-ICV-status interaction terms. This general linear model can be expressed as:

$$\pi_{ijt} = \beta_0 + U_{0i} + U_{0j} + ICV_{ijt}\beta_1 + FU_{ijt}\beta_2 + ICVxFU_{ijt}\beta_3 + \mathbf{x}'_{ijt}\boldsymbol{\gamma} + \mathbf{z}'_j\boldsymbol{\zeta} + \varepsilon_{ijt}$$

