where:  $\pi_{ijt}$  denotes the linearized expected outcome for participant  $i$  at SSP site  $j$  on occasion  $t$ ;  $\beta_0$  is the overall intercept;  $U_{0i}$  and  $U_{0j}$  are normally distributed person-level and site-level random intercepts;  $ICV_{ijt}$  is an indicator for participation being at an ICV site,  $FU_{ijt}$  is a binary indicator for the 6-month follow-up assessment;  $ICVxFU_{ijt}$  is an ICV-by-follow-up interaction term;  $\mathbf{x}_{ijt}$  is a vector of participant-level covariates with  $\boldsymbol{\gamma}$  the vector of corresponding fixed-effects regression parameters;  $\mathbf{z}'_j$  is a vector of SSP site covariates (including intervention phase) with  $\boldsymbol{\zeta}$  the vector of corresponding fixed effects; and  $\varepsilon_{ijt}$  are error terms. The null hypothesis of no significant group-by-time interaction at the follow-ups can be tested using a 1-df F-test of  $H_0: \beta_3 = \mathbf{0}$ . The form of  $\pi_{ijt}$  and the expected distribution of the residuals will be specified based on the specific outcome. For the composite outcome, we will use mixed effects linear regression with an identity link function and normally distributed residuals.

The above-described model does not have a coefficient for matched-pair, and therefore “breaks the pairing.” This approach may be more statistically powerful when the matching accounts for little variability among clusters, and we expect that to the case given the limited information that was available for conducting the matching. How much variability is accounted for by the matching will be based on reduction in the variance of the cluster-level random intercept when including fixed effects for matched-pairs, and a likelihood ratio test comparing models with and without fixed effects for matched-pairs.

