For the dichotomous outcome of MOUD use in the last 30 days, we will follow the same general formula described above using mixed effects logistic regression with a logit link function and a binomial residual distribution. Outcome analyses will be preceded by preliminary analyses examining bias in intervention assignment and potential baseline confounders of the relationship between assignment and the primary outcomes. We shall evaluate and adjust for any potential confounders in adjusted outcome analyses. All analyses will be conducted in Stata and will include the use of the random effects gllamm procedures with Huber/White variance-covariance estimators.

The composite PWID score will be calculated for each participant at each study visit according to the rubric in the **Appendix**, where a higher score indicates higher risk for adverse events or lower use of evidence-based PWID services. At the follow-up visits, we will calculate each participant's change in score from baseline. We will estimate the association between ICV cluster and change in the score with a multi-level linear regression model, similar to that shown above. In a supplementary analysis, we will convert follow-up scores to binary outcomes that indicate whether the score has decreased from baseline (improved) or not. In this case we will use a logistic regression model.

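### Huber/White standard errors are prescribed for 12 randomised sites with no denominator df, small-sample correction or alpha; clustered by site with independent sites, they give about 6-10% false positives at an assumed 5% level

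*Combined protocol and SAP*

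**What the plan says.** Sections 6, 12.1 and 12.5 describe a two-arm trial with 12 sites in 6 pairs, one site per pair in each arm. Section 12.5 recognises the small number of units and answers it by matching: "Because the number of randomly allocated units in this cluster randomized trial is small, we anticipate using a matched-pair design".

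Section 12.7.1 then specifies the following.

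- Correlation within sites and participants: "this will be addressed by using random intercepts for site and random intercepts for participants".
- The test: "The null hypothesis of no significant group-by-time interaction at the follow-ups can be tested using a 1-df F-test of" β3 = 0. Only the numerator df is given.
- The pairs: "The above-described model does not have a coefficient for matched-pair, and therefore" gives up the pairing. The reason offered is that matching should explain little between-site variability: "we expect that to the case given the limited information that was available for conducting the matching".
- Site covariates: the z term "is a vector of SSP site covariates (including intervention phase) with" its own fixed effects.
- Standard errors: all analyses "will include the use of the random effects gllamm procedures with Huber/White variance-covariance estimators".
- Further on in the same section, a change-score analysis of the composite: "We will estimate the association between ICV cluster and change in the score with a multi-level linear regression model".

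No section states the clustering level of the robust errors, a denominator df, a small-sample correction, or alpha.

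**The concern.** A robust variance clustered by site is estimated from the spread of 12 site-level contributions. With so few, it is biased downward and is itself noisy, so both the variance and the reference distribution need correction. The plan prescribes the estimator but neither correction.

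The primary p-value and confidence interval are at stake. Suppose the uncorrected site-clustered statistic is 2.2. With a normal reference, p = 0.028. With a 12/11 factor and t on 10 df, 2.2/√(12/11) = 2.106 and p = 0.061. A t-test on the same 12 site means has 2.2 × √(5/6) = 2.008 and p = 0.072. For uncorrected statistics between 1.96 and 2.44 (= 2.228/√(5/6)), the normal reference and the site-mean t-test disagree at 5%.

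**Working it through.** **Inputs.** From the documents: 6 v 6 sites, 60 enrolled per site, 80% retention (48 followed per site, 288 per arm), site SD .22, participant SD 1.05, effect .33 SD, 80% power. Assumed because not stated: two-sided alpha 0.05, normal data, residual SD 1. Let τ be the SD of a site's true mean change. The documents give no value, so 0 to 0.22 is used as a range.

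**1. The plan's own figure.** Time-constant random intercepts cancel in within-person change, whose variance is 2 × 1² = 2. The variance of the arm difference is v = 2 × 2/(6 × 48) = 0.01389, so .33/√0.01389 = 2.800. With a normal reference, power = P(Z > 1.960 − 2.800) = 0.80. The stated 80% is therefore reproduced with residual SD 1, τ = 0 and a normal reference. Section 12.4 states none of these, so the match is not proof that they were used.

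**2. Bias of the site-clustered sandwich.** Let s1² and s0² be the sample variances of the six site means in each arm.

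- Sandwich: (5/36)(s1² + s0²)
- Unbiased: (1/6)(s1² + s0²)
- Ratio f = (5/36)/(1/6) = 5/6, or 10/11 after a 12/11 factor

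The ratio does not depend on τ or the residual SD.

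**3. False-positive rate, independent sites.** The unbiased statistic follows t on 10 df, so the rate with critical value c is P(|t10| > c√f).

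| Reference | c | f = 5/6 | f = 10/11 |
|---|---|---|---|
| Normal | 1.960 | 10.4% | 9.1% |
| t, 11 df | 2.201 | 7.2% | 6.2% |
| t, 10 df | 2.228 | 6.9% | 6.0% |

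Relative interval width is c√f/2.228. It runs from 1.960 × √(5/6)/2.228 = 0.803 to √(10/11) = 0.953, so intervals are 5-20% too narrow. Simulating the displayed two-visit model (20,000 trials per scenario) gave 9.8-10.2% uncorrected with a normal reference, and 5.5-6.0% with 12/11 and t.

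**4. If paired sites share variance.** With half of τ² common to a pair (1,000,000 draws of 12 site means), the uncorrected normal rate is 8.9% at τ = 0.10 and 6.4% at τ = 0.22. With 12/11 and t it is 4.9-5.1% and 3.3-3.5%.

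**5. Intervention phase.** In the displayed model phase is a main effect, not crossed with follow-up, so it takes no df from β3. Simulated uncorrected normal rates were 9.7-10.0% with phase and 9.6-10.6% without. If phase enters a change-score or site-mean regression as three recruitment waves (assumed from the staggering in section 12.5), f = 2/3 on 8 df. The rates are then 13.3-14.8% (normal) and 9.4-11.0% (t on 10-11 df).

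**6. Secondary: clustering by participant.** The displayed model has no site-by-follow-up term, so the reported variance is v while the true variance is v + τ²/3. The rate is 2P(Z > 1.96√(v/(v + τ²/3))): 5.0%, 7.8%, 11.4% and 18.3% at τ = 0, 0.10, 0.15 and 0.22 with independent sites.

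Binary and ordinal outcomes were not computed.

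**The case against.** Several counter-arguments carry weight.

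- **An F-test implies finite denominator df.** If that means t on 10-11 df, the excess is 1.0-2.2 percentage points, and with 12/11 and shared pair variance it can vanish or reverse. This stands, but the plan fixes neither the df nor the factor, and it expects matching to explain little, which makes independent sites its own working assumption.
- **The plan models clustering.** It does, through site and participant intercepts, and a reader should not infer that clustering is ignored. The gap lies in the robust error and its reference distribution. The intercepts are also constant over time, so they do not describe site differences in change.
- **The primary test is specified.** A reader might infer that the primary p-value is undefined. That goes too far: section 12.7.1 gives the model, link, residual distribution, null hypothesis and test. Missing are alpha, the denominator df, the correction, and a statement whether the displayed or the change-score model gives the primary result. The plan calls these two models similar.
- **Participant clustering is the weaker reading.** A three-level model with a site effect makes sites the independent units, and the documents give no τ. The SD of .22 in section 12.4 belongs to a site's level, not its change. A reader might take 18% as the expected error rate, and the documents do not support that.

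**Conclusion.** The concern holds. With six sites per arm, uncorrected site-clustered Huber/White errors give 10.4% false positives with a normal reference (9.1% with 12/11) and 6.9-7.2% with t on 10-11 df (6.0-6.2% with 12/11), against an assumed two-sided 5%. These rates rest on site clustering, independent sites, balance and normal data. They do not depend on the residual SD or τ.

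They should not be read as a fixed inflation. Shared pair variance lowers them, below 5% in some cases with 12/11 and t, while phase in a change-score regression raises them. Nor does keeping phase always leave 8 df: as a main effect in the two-visit model it costs the interaction test none.

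The participant-clustered range of about 8-18% at τ = 0.10-0.22 is secondary and illustrative.

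**What to change.** 1. State alpha and sidedness, and name which of the two models in section 12.7.1 gives the primary result.
2. Do not use uncorrected Huber/White errors for the ICV effect. Use either (a) a t-test on the 12 site-mean changes with 10 df, or (b) a REML mixed model with a site-by-follow-up random effect and Kenward-Roger or Satterthwaite df, without manual df subtraction.
3. Reduce df for phase (to 8 with three waves) only if phase enters a change-score or site-mean regression.
4. For binary and ordinal outcomes use site-level summaries, or a bias-corrected site-clustered sandwich with a t reference.
5. Report a paired t-test on the 6 pair differences (5 df) as a sensitivity analysis.

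**Cost.** SAP wording and code; no new data. Intervals widen. Both options can be conservative if pairs share variance. With half of τ² shared, (a) rejects in 4.1% and 2.7% of null trials at τ = 0.10 and 0.22, and (b) in 2.6-3.3%. With independent sites, (a) holds 5.0% and (b) gives 3.3-5.0%. The paired test held 5.0% throughout.

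The power in section 12.4 should be recomputed under the chosen test. On the assumptions of step 1 (residual SD 1, τ = 0), it is about 71% with t on 10 df instead of 80%, and about 61% for the paired test. These figures are illustrations, because section 12.4 states none of those assumptions.

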**Study Size:**

The study will be conducted at 12 neighborhood sites or clusters in Baltimore that are visited by the SSP. We aim to enroll 60 participants at each site (720 participants overall).

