#### **12.4 Sample Size Considerations**

To estimate the power to correctly reject a null hypothesis, we used simulation methods assuming a normally distributed composite PWID score. We adapted the methods of Arnold et al. for using mixed effects logistic regression random intercepts for cluster (SD = .22) and participant (SD = 1.05) with one baseline and one follow-up assessment, 80% retention, and a similar treatment effect at each follow-up. With an initial sample size of 720 participants, we would have 80% power if the true person-level composite scores were .33 standard deviations higher at follow-up at the target sites than at the control sites, controlling for composite scores at baseline, random variation across study sites, and random variation across individuals. Using Cohen's criteria, this would correspond to a small-medium effect size.

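### Section 12.7.1 leaves the primary contrast for the composite score open and defines ICV in two ways; one model with equal baseline means would settle both and gain some precision

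*Combined protocol and SAP*

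**What the plan says.** Section 9.3.4 bases the primary analysis on baseline and the 7-month visit (labelled a 6-month assessment in 12.7.1). For that pair of visits, Section 12.7.1 describes two analyses of the composite score.

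- **Repeated measures.** A three-level model has random intercepts for site and participant, an ICV term (beta1), a follow-up term (beta2) and their product (beta3). "The null hypothesis of no significant group-by-time interaction at the follow-ups can be tested using a 1-df F-test", that is, of beta3 = 0.
- **Change score.** Later in the same section: "We will estimate the association between ICV cluster and change in the score with a multi-level linear regression model". The text calls this model similar to the earlier one. No baseline covariate is mentioned.

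Neither is designated primary. The ICV term is also described twice: before the equation as an exposure status that changes over time, and below the equation as an indicator of being at an ICV site.

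Section 12.4 describes its simulation as having "random intercepts for cluster (SD = .22) and participant (SD = 1.05) with one baseline and one follow-up assessment, 80% retention". Its target is 80% power to detect a 0.33 SD difference between arms at follow-up when 720 people are enrolled. The comparison is said to be made while "controlling for composite scores at baseline, random variation across study sites, and random variation across individuals".

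Sections 6 and 7.2 place recruitment before randomization. Under Section 12.6 a pair's allocation is withheld until the pair is fully or almost fully enrolled.

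**The concern.** Two things are left open, and they interact.

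**Which model.** Read as exposure, ICV is 0 for everyone at a baseline that precedes allocation. With one baseline and one follow-up, the ICV column and the ICV-by-follow-up column are then identical, and beta3 has no estimate separate from beta1. Read as site membership, the model is identified, but beta1 is a freely estimated baseline arm difference. The change score makes the same kind of comparison, a difference in differences, using completers only.

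**Precision.** When baselines precede disclosure of allocation, the expected baseline arm difference is zero. Estimating it, or subtracting it in full, spends information. The plan already collects what is needed to avoid this.

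At stake are a primary test somewhat less precise than the data allow, and a choice between analyses that agree with complete data but can differ once some participants lack follow-up.

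**Working it through.** **Inputs**

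- From the plan: 12 sites, 6 per arm (12.5); 60 enrolled per site (Study Size); site SD 0.22, participant SD 1.05, 80% retention, effect 0.33 (12.4). Follow-up records per site: 0.8 × 60 = 48.
- Assumed because not stated: residual SD r = 1, alpha 0.05 two-sided, normal reference, no site-by-visit variance, variance components treated as known.

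Within a site, the variance of one score is V = 1.05² + 1² = 2.1025, and the within-person correlation is rho = 1.1025/2.1025 = 0.5244. An arm contrast has variance (2/6) × the per-site variance.

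**1. Reproduce the plan's 80% (change score).** Site and person intercepts cancel.

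- Per site: 2r²/48 = 0.041667
- Contrast: 0.041667/3 = 0.01389, SE 0.1179
- 0.33/0.1179 = 2.80; power = Phi(2.80 − 1.96) = 79.96%

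**2. Interaction model, ICV as site membership, all baselines used.** The 12 participants per site without follow-up still inform the baseline mean.

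- Baseline mean: V/60 = 0.035042
- Follow-up mean: V(1 − rho²)/48 + rho²V/60 = 0.031758 + 0.009635 = 0.041393
- Covariance: rho × V/60 = 0.018375
- Per site: 0.035042 + 0.041393 − 2 × 0.018375 = 0.039685
- Contrast: 0.01323, SE 0.1150, power 81.8%

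**3. Same model with equal baseline means (no ICV main effect).** Site variance 0.22² = 0.0484 now enters each term.

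- Baseline variance 0.083442; follow-up variance 0.089793; covariance 0.066775
- Best weight on the baseline difference: 0.066775/0.083442 = 0.80, where the interaction model uses 1
- Per site: 0.089793 − 0.066775²/0.083442 = 0.036356
- Contrast: 0.01212, SE 0.1101, power 85.0%

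**4. Savings**

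- Against the interaction model: 1 − 0.012119/0.013228 = 8.4%
- Against the change score: 1 − 0.012119/0.013889 = 12.7%
- The effect detectable with 80% power falls from 0.330 (change score) or 0.322 (interaction) to 0.308.
- With completers only, the constrained model has 84.5% power against 80.0%, so most of the gain over the change score does not come from the extra baselines.

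**5. Sensitivity of the saving against the interaction model**

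| Site SD | Residual SD | Saving |
|---|---|---|
| 0.22 | 0.7 | 4.5% |
| 0.22 | 1.0 | 8.4% |
| 0.22 | 1.5 | 15.4% |
| 0.40 | 1.0 | 3.6% |

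With a t reference on 10 df the three powers are 71.4% (change score), 73.5% (interaction) and 77.1% (constrained). The order is unchanged; the choice of reference distribution is a separate question.

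**6. Person-level baseline adjustment.** Regressing follow-up on the individual baseline score with a random site intercept gives SE 0.119 and power 79.0% at residual SD 1. That is no gain, because it removes the constant site effect only in part.

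**The case against.** A reader might infer that the trial was powered on a baseline-controlled analysis and that the specified test falls short of it. The documents do not support that. Step 1 reaches the stated power with the change score alone, and the interaction model slightly exceeds it. Nor is a contradiction between 12.4 and 12.7.1 shown: Section 12.4 has random intercepts for site and participant and one visit of each kind, which is the structure of the 12.7.1 model. A participant intercept in a repeated-measures model is one ordinary way of controlling for baseline. Section 12.4 mentions neither a baseline covariate nor a constraint on the means.

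It can also be said that the time-varying definition, once its redundant term is dropped, already gives the constrained model. That is right, and it shows that the fix is close to one reading of the plan. But the plan does not drop the term, and its other definition leads to a different model.

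The strongest objection concerns robustness. Allocation may be disclosed when a pair is only nearly enrolled, and the intervention is unmasked, so a few baselines may follow disclosure. The interaction model passes none of a persistent baseline arm difference into the effect. The constrained model passes 1 − 0.80 = 20% at residual SD 1, and 36% at 1.5. This stands, and it is why a sensitivity analysis belongs in the fix.

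On attrition, Section 12.7.1 already plans multiple imputation if predictors of missingness are found. That limits any divergence between the two analyses but does not say which is primary.

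**Conclusion.** The point holds as a clarification with a modest gain in precision. Section 12.7.1 offers two analyses of the composite score without naming one as primary. Its two definitions of ICV lead either to a model whose coefficients cannot be separated or to one that estimates a baseline difference whose expected value is zero by design.

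The cost is forgone precision, not power below the stated 80%. At residual SD 1 it is 8.4% of the variance against the interaction model and 12.7% against the change score. Against the interaction model it is 4.5% to 15.4% for residual SD 0.7 to 1.5, and less if sites differ more than planned. These figures rest on the unstated residual SD, a two-sided 0.05 level and no site-by-visit variance. The constraint also needs baselines to precede disclosure of the pair's allocation.

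**What to change.** In Section 12.7.1:

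- Name one primary analysis: the three-level mixed model on the baseline and 7-month composite scores, with random intercepts for site and person, a visit effect and a single ICV-by-visit term. Omit the ICV main effect, and give the reason: baselines precede allocation. Test the ICV-by-visit coefficient.
- Define ICV once, to match that model.
- Make the change-score regression supportive.
- As a sensitivity analysis, report the model with the ICV main effect, or the primary model without participants enrolled after their pair's allocation was disclosed.

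In Section 12.4, align the wording on baseline with this model, and state the residual SD, the significance level and which SD the 0.33 refers to.

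The cost is revised wording, one removed model term and one extra analysis, with no new data. Excluding late enrollees would also require the disclosure date for each pair. The downside is the reliance on baselines that precede disclosure, which the sensitivity analysis addresses.

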### **9.3.4 *COVID-19 Impact on Study***

The COVID-19 pandemic initially struck Baltimore, MD in March 2020 and had substantial effects on this study. The pandemic led to suspension of both study cohort follow-up visits and the ICV intervention for many months. The study achieved full enrollment (N=720, n=60 at each of the 12 sites) between July 2018 and August 2019. Two cohort follow-up visits were planned at 7 months and 14 months. At the time of pandemic-related shut downs we had completed the 7-month visits at all 12 sites. Additionally, we had completed the 14-month visit at 4 of the 12 sites. We switched to telephone-based follow-up visits, which included the participant survey but not laboratory tests. We also added questions to assess the effects of COVID-19 among the study cohort. We resumed in-person visits in July 2021. For the purposes of this trial, we decided to base primary analyses on the baseline visit and the first follow-up visit (7 months). Although this does not include the longer follow-up that we planned, it includes only data that was collected prior to the pandemic. In secondary analyses we will consider data collected during and after pandemic-related shut downs.

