We are aware of the risk of attrition in this study, and our sample size estimates have accounted for up to 20% attrition, despite intensive retention efforts. We will examine whether missingness is associated with observed data using standard methods. If we do identify predictors of missingness (i.e., data are not missing completely at random [MCAR]), we will conduct a second set of outcome analyses using multiple imputation to evaluate the robustness of the primary outcome analyses to missingness and report estimates based on multiple imputation that would be valid based on the assumption that the data are missing at random (MAR) as opposed to not missing at random (NMAR). As missing data are expected to follow multiple distributions, we will impute using chained equations. We will produce imputed datasets ( $m > 10$ ), run outcome analyses on all sets, and derive point and standard error estimates for treatment effects and other parameters from the distribution of estimates from the outcome analyses with imputed datasets. We will implement multiple imputation using the Stata "mi impute chained" and "mi estimate" procedures.

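### The only missing-data check is MAR imputation, run only if dropout has observed predictors; it cannot show robustness to dropout that depends on the unseen 7-month score

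*Combined protocol and SAP*

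**What the plan says.** Section 12.7.1 describes the primary analysis in two ways. The first is a three-level model with random intercepts for site and participant, fitted to the baseline and follow-up scores: "For the composite outcome, we will use mixed effects linear regression". The second, later in the section, is a multi-level regression of each participant's change from baseline. Section 9.3.4 restricts the primary analysis to one follow-up: "we decided to base primary analyses on the baseline visit and the first follow-up visit (7 months").

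On attrition, Section 12.7.1 says that "our sample size estimates have accounted for up to 20% attrition". It will examine whether missingness is related to observed data. The next step is conditional: "If we do identify predictors of missingness (i.e., data are not missing completely at random [MCAR"), then "we will conduct a second set of outcome analyses using multiple imputation to evaluate the robustness of the primary outcome analyses to missingness". The section adds that the imputed estimates hold under MAR and not under NMAR (missingness that depends on the unseen value). The method is chained equations with more than 10 imputed data sets. The variables in the imputation model are not listed.

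No delta-adjusted, tipping-point, pattern-mixture, selection-model or worst-case analysis is planned. Confirmed deaths score 15 under the Appendix rubric, so they are not missing data.

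**The concern.** The trial is unmasked, allows for substantial attrition, and follows people whose relapse or incarceration could both worsen the 7-month score and prevent the visit. If that link differs between arms, the estimated ICV effect is biased.

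The planned check has two gaps. First, imputation under MAR cannot detect such dropout. A mixed model fitted by likelihood to all baseline and follow-up scores is already valid under MAR given its own variables, so imputing from those same variables gives nearly the same answer, and their agreement could be read as robustness. Second, the check runs only if observed data predict missingness. A test that finds no predictor does not establish that dropout is unrelated to the unseen score, but the plan then stops.

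**Working it through.** **Inputs from the documents.** Section 3, Study Size: "We aim to enroll 60 participants at each site (720 participants overall"), so 360 per arm. Section 12.4: "random intercepts for cluster (SD = .22) and participant (SD = 1.05) with one baseline and one follow-up assessment, 80% retention"; and "we would have 80% power if the true person-level composite scores were .33 standard deviations higher at follow-up at the target sites". With 80% retained, 360 × 0.8 = 288 per arm have a follow-up score, and 720 × 0.2 = 144 do not.

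**Assumptions.** Residual SD σ, alpha and sidedness are not stated. I take σ = 1 and a two-sided 0.05 test with critical value 1.96, and read 0.33 on the scale where σ = 1.

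**Step 1: reproduce the plan's power.** Site and participant intercepts cancel in a change score, so for the difference in change among completers:

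SE = √(2 × 2σ²/n) = 2σ/√n = 2/√288 = 0.1179

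Power = Φ(0.33/0.1179 − 1.96) = Φ(0.84) = 79.96%, against 80% stated. A mixed model that also uses non-completers' baselines gives 81.8%. The match depends on σ: power runs from 94% at σ = 0.8 to 65% at σ = 1.2. A t reference with 10 df gives 71%.

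**Step 2: tipping point.** If a fraction p of the ICV arm is missing and those scores are on average worse by δ than MAR predicts, the benefit falls by pδ. Significance is lost at

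δ = (estimate − 1.96 × SE)/p

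With SE held at 0.1179, 1.96 × SE = 0.231.

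| Estimate | p | δ that removes significance | δ that gives zero effect |
|---|---|---|---|
| 0.33 | 10% | 0.099/0.10 = 0.99 | 3.3 |
| 0.33 | 20% | 0.099/0.20 = 0.50 | 1.65 |
| 0.33 | 30% | 0.099/0.30 = 0.33 | 1.1 |
| 0.28 | 20% | 0.049/0.20 = 0.24 | 0.28/0.20 = 1.4 |

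If SE is recomputed for the completers, 10% missing gives SE = 2/√324 = 0.111 and δ = (0.33 − 0.218)/0.10 = 1.12; 30% missing gives SE = 2/√252 = 0.126 and δ = (0.33 − 0.247)/0.30 = 0.28. For the uncertainty in σ, at 20% missing: σ = 0.8 gives (0.33 − 0.185)/0.20 = 0.73, and σ = 1.2 gives (0.33 − 0.277)/0.20 = 0.26.

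**Step 3: does MAR imputation move the estimate?** Simulation of 12 sites of 60, SDs 0.22, 1.05 and 1, true effect −0.33 (lower is better), 20% missing per arm, 600 runs, Monte Carlo SE about 0.005. In the last three rows the stated dependence is in the ICV arm only.

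| Dropout depends on | Completer change score | Likelihood, all baselines | MI, same variables | MI with auxiliary variable |
|---|---|---|---|---|
| Nothing | −0.330 | −0.330 | −0.330 | −0.329 |
| Baseline score | −0.189 | −0.319 | −0.319 | −0.320 |
| A variable outside the outcome model | −0.450 | −0.448 | −0.448 | −0.329 |
| The 7-month score itself | −0.458 | −0.535 | −0.534 | −0.488 |

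In the last row the likelihood and same-variable MI estimates correlate at 0.997 across runs and are wrong by the same amount. Sixty runs with a fitted mixed model (participant intercept only) gave −0.550, against −0.556 after imputation. A separate simulation with no true effect, and ICV-arm dropout rising with the unseen follow-up deviation (log-odds 0.6 per SD), gave a false benefit of 0.108 by likelihood and 0.107 by MI.

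**Step 4: the trigger.** Testing arm and baseline score as predictors, the trigger fired in about 10% of runs when dropout followed the follow-up deviation alone, against 9.5% with no bias. When dropout followed the actual 7-month score (log-odds 0.6 per SD), it fired in 42 to 44% of runs if this held in the ICV arm only, and in 90 to 91% if it held in both arms.

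**The case against.** A reader might infer that the imputation merely repeats the primary model's assumption and can test nothing. The documents do not support that. Against the completer change-score regression, MI relaxes the assumption (second row of the simulation table: −0.189 becomes −0.319, truth −0.33). Against the mixed model it would also do so if the predictors of missingness enter the imputation (third row: −0.448 becomes −0.329). That is a natural reading of a procedure started by finding predictors, although the plan does not say it.

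A reader might also infer that the plan claims validity under NMAR. It does not: it confines the imputed estimates to MAR.

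Nor should the 10% trigger rate be generalised. In that scenario dropout follows a deviation that is independent of observed data by construction. The firing rate is far higher when dropout follows the actual score, and testing many questionnaire variables raises it by chance: 20 independent null tests at 5% fire with probability 1 − 0.95²⁰ = 64%. One can add that skipping plain MAR imputation under pure NMAR loses nothing, because it would not have detected the problem.

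Finally, the simulated bias is one-sided by choice. With the same mechanism in both arms it was about zero (−0.011 to +0.007). No document shows that dropout differs by arm, 20% is an upper allowance, and the Appendix scores confirmed deaths and supplements emergency department use from external records.

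All of this stands, and it limits the size of the point. What it leaves untouched is that no planned analysis addresses dropout that depends on the unseen score, whether or not the trigger fires. Firing more often leads only to the same MAR analysis.

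**Conclusion.** The point holds as a cheap improvement to the plan; it does not show that the primary result will be biased. Conditional MAR imputation is the only sensitivity analysis for missing outcomes. It is useful against the change-score regression, of little use against the mixed model without auxiliary variables, and uninformative about NMAR dropout in either case.

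At the plan's own design point the result would be moderately sensitive: about 0.5 SD at 20% missing, about 1.0 SD at 10%. These figures rest on residual SD 1, a normal critical value and a shift confined to the ICV arm. The simulated biases illustrate a mechanism and are not predictions. The direction of any real bias is unknown.

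**What to change.** - Remove the MCAR trigger and always run the imputation.
- List the imputation variables. Include the observed predictors of missingness as auxiliary variables; candidates are the baseline questionnaire domains, the 3-month check-in contact (Section 7.3) and the external treatment records (Section 12.2). Account for site, for example with site indicators.
- On those data sets, run a prespecified delta-adjusted analysis of the 7-month composite score. Shift the imputed scores toward worse over a stated grid, for example 0 to 1 SD, in the ICV arm only, the control arm only and both arms. Refit the primary model and report the shift at which the conclusion changes.
- Keep confirmed deaths scored by the rubric and outside the imputation.
- Describe the plain MAR imputation as a check under MAR only.

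The cost is a few lines of Stata on imputations already planned, plus one table. Sample size and data collection do not change: Section 9.3.4 reports the 7-month visits as completed at all 12 sites, so the analysis is the only place left to address this. The downside is that a marginal result may have to be reported as fragile.
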